6.13 PSYCHOMETRIC ANALYSIS OF THE PGI-S ITEMS

The following analyses will be conducted on the PAP.

6.13.1 *Validity of the PGI-S Items*

A number of specific forms of validity exist, but one of the most important to the present study is construct validity, which describes the relationships among multiple indicators of a construct and the degree to which they follow predictable patterns. Correlations will be computed between PGI-S scores and in Borg Dyspnea scores, oxygen saturation, and HR. The goal is to

demonstrate stronger relationships among measures addressing similar constructs as compared with measures addressing more disparate constructs. Correlations will be computed using data collected at the same or nominally similar time points, specifically, at Baseline (pre-ISWT average of -15 minutes and 0 minutes) and post-ISWT (1, 2, 3, 4, and 5 minutes).

Inferences regarding validity are based on the patterns of correlations among the measures. Cohen (1992) provides the following guideline for interpreting correlation coefficients: absolute values of correlations of 0.50 or greater are considered strong, correlations that fall between 0.30 and 0.49 are moderate, and those between 0.10 and 0.29 are small.

Higher scores on the PGI-S items, Modified Borg scale, and HR indicate worse outcomes, while higher oxygen saturation is a better outcome. Therefore, positive correlations are expected between the PGI-S items and the Modified Borg scale and HR, and negative correlations are expected between the PGI-S items and oxygen saturation. Furthermore, the following are hypothesized:

- The PGI-S Overall item will be at least moderately correlated ($|r| > 0.30$) with oxygen saturation and with HR
- The PGI-S Shortness of Breath item will be at least moderately correlated with the Modified Borg score, oxygen saturation, and HR
- The PGI-S Physical Fatigue item will be at least moderately correlated with oxygen saturation and HR

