To further support the construct validity of the PGI-S, correlations will also be computed between PGI-S change scores and change in Borg Dyspnea scores, oxygen saturation, and HR. These correlations will allow us to evaluate potential improvements (or declines) in the severity of symptoms commonly associated with PAH (as assessed by the PGI-S) and any corresponding improvements (or declines) in subjects' clinical measures. Correlations will be computed between changes from Baseline (pre-ISWT average of -15 minutes and 0 minutes) and post-ISWT (1, 2, 3, 4, and 5 minutes). Similar to the cross-sectional construct validity hypotheses, it is expected that:

- Change in the PGI-S Overall item will be at least moderately ($|r| > 0.30$) negatively correlated with change in oxygen saturation and at least moderately positively correlated with change in HR

- Change in the PGI-S Shortness of Breath item will be at least moderately positively correlated with change in the Modified Borg score and with change in HR, and at least moderately negatively correlated with change in oxygen saturation
- Change in the PGI-S Physical Fatigue item will be at least moderately negatively correlated with change in oxygen saturation and at least moderately positively correlated with change in HR

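### SAP 6.13.1 names an ordering of correlations as its validity goal, but its Shortness of Breath hypotheses only set one common floor and never compare the correlations

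*SAP*

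**What the plan says.** SAP 6.13.1 treats construct validity as one of the most important forms of validity for this study. It states the goal as an ordering, to "demonstrate stronger relationships among measures addressing similar constructs as compared with measures addressing more disparate constructs", and adds that "Inferences regarding validity are based on the patterns of correlations among the measures". For reading coefficients it supplies bands: "absolute values of correlations of 0.50 or greater are considered strong, correlations that fall between 0.30 and 0.49 are moderate".

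The hypotheses that follow are lower bounds with a sign.

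- **Level scores:** "The PGI-S Shortness of Breath item will be at least moderately correlated with the Modified Borg score, oxygen saturation, and HR". The numerical meaning of moderate is given in the bullet before it: "The PGI-S Overall item will be at least moderately correlated ($|r| > 0.30$) with oxygen saturation and with HR". The expected signs are positive for Borg and HR and negative for SpO2.
- **Change scores:** "Change in the PGI-S Shortness of Breath item will be at least moderately positively correlated with change in the Modified Borg score". The same bullet sets the same floor for HR, and for SpO2 with a negative sign.

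No bullet ranks one correlation above another. Only the Shortness of Breath item carries a Borg expectation. Nothing is said about how its correlation with Borg should compare with that of the Physical Fatigue item. SAP 6.10 lists hypothesis testing as not applicable.

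**The concern.** Borg is plainly the similar construct here. SAP 5.1 describes both PGI-S and Borg as self-ratings of the present moment, and the Borg script in SAP section 9 asks about shortness of breath. SpO2 and HR are oximeter signals. The stated goal therefore predicts that the Shortness of Breath item will follow Borg more closely than it follows SpO2 or HR. It also predicts that the item will follow Borg more closely than the Physical Fatigue item does.

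The hypotheses set one floor for all three comparators, and a floor cannot carry that prediction. All of them may be met when the goal is not supported, and some may fail when it is. Psychometric characterisation is the primary objective, and the protocol's clinical hypothesis is that these questions can serve as endpoints in clinical studies. A report that the hypotheses were met could be read as evidence for a pattern that was never examined.

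**Working it through.** There is no planned figure to reproduce, because the SAP gives no power or precision for the correlations. The main check is one of logic; steps 2 and 3 illustrate its size.

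**Inputs from the documents.** Floor |r| > 0.30 with the expected sign (SAP 6.13.1); 36 evaluable subjects (SAP section 4); Borg collected at -15 and 0 minutes before the ISWT and at its completion (SAP 5.1.2).

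**Assumed, because the documents do not give them.** One observation per subject; multivariate normal data; Borg-SpO2 -0.3, Borg-HR 0.3 and SpO2-HR -0.4.

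**1. Can the hypotheses and the goal disagree?** Apply the floor to each pattern. Then ask whether r(Borg) exceeds both |r(SpO2)| and |r(HR)|.

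| Borg | SpO2 | HR | All floors met | Ordering holds |
|---|---|---|---|---|
| 0.35 | -0.45 | 0.45 | yes | no |
| 0.31 | -0.60 | 0.60 | yes | no |
| 0.35 | -0.35 | 0.35 | yes | no |
| 0.60 | -0.35 | 0.35 | yes | yes |
| 0.70 | -0.20 | 0.20 | no | yes |

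A correlation matrix is possible only if its smallest eigenvalue is not negative. The smallest eigenvalues for the first two rows are 0.53 and 0.33, so both reversed patterns can occur. In the second row the other dyspnea rating is moderate on the SAP's own bands while both physiological signals are strong.

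**2. How often would this happen with 36 subjects?** Results of 40,000 simulated studies for each set of true values:

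- True 0.35/-0.45/0.45: all three floors are met in about 51% of studies, and in about 82% of those Borg is not the strongest correlate.
- True 0.31/-0.60/0.60: met in 52%, and in 98% of those Borg is not the strongest.
- True 0.70/-0.20/0.20: met in about 12%, although Borg is the strongest in over 99% of all studies.

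The percentages move with the assumed values. The disagreement shown in step 1 does not.

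**3. Can the ordering be read off the table by eye?** The separate interval for each correlation is tanh(atanh r ± 1.96/√(n - 3)). With n = 36:

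- r1 = 0.60 (Borg): 0.338 to 0.776
- r2 = 0.35 (HR): 0.024 to 0.609

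The two correlations share the PGI-S item, so they are dependent. With r12 the Borg-HR correlation, the correlation between the two estimates is

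c = [(r12 - r1·r2/2)(1 - r1² - r2² - r12²) + r12³] / [(1 - r1²)(1 - r2²)]

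= [(0.30 - 0.105)(1 - 0.36 - 0.1225 - 0.09) + 0.027] / (0.64 × 0.8775) = 0.197.

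The difference is 0.25. Its limits combine the distances from each estimate to its own limits:

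- Lower: 0.25 - √(0.262² + 0.259² - 2 × 0.197 × 0.262 × 0.259) = 0.25 - 0.330 = -0.08
- Upper: 0.25 + √(0.176² + 0.326² - 2 × 0.197 × 0.176 × 0.326) = 0.25 + 0.339 = 0.59

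The same method for 0.35 versus 0.45 gives a difference of -0.10. Its 95% CI runs from about (-0.51, 0.32) with a Borg-HR correlation of 0 to about (-0.41, 0.20) with a correlation of 0.5. Two coefficients set side by side do not settle which is larger.

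**The case against.** The strongest reply is that the SAP makes no formal decision on these bullets. They are added expectations in a descriptive study, inference is said to rest on the pattern, and every coefficient needed will be tabulated. A Borg correlation below the HR correlation would be visible and would count against the stated goal. This stands. A reader might infer that the plan would declare the dyspnea item valid once the floors are met, but the documents contain no such rule.

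A reader might also infer that the plan cannot show that the three items differ. That is not supported either. SAP 6.9 and protocol 10.3.2 plan correlations among the three items, and SAP 6.13.1 correlates PGI-S scores in general with Borg, so Physical Fatigue-Borg will be available.

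A third tempting step is to require r of at least 0.50 between Shortness of Breath and Borg. That is a matter of choice: at least moderate already includes strong. The documents also give reasons for attenuation. Symptoms are expected to be minimal at baseline (SAP 6.13.2), and inclusion criterion 5 requires a Borg change of at least 1 point, which may narrow the range of change scores.

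Finally, the example of 0.35 against 0.45 lies within sampling error, as step 3 shows, so it does not demonstrate a reversal in any actual study. It shows only that the hypotheses do not test the ordering. The imprecision is itself the reason to report an interval for each difference.

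**Conclusion.** The concern holds in limited form. The Shortness of Breath hypotheses, for level and for change, can all be met by a pattern that does not support or even reverses the stated goal, and can fail under one that supports it. This follows from the wording alone and needs no assumption. The sizes (for example, about 12% of studies meeting all floors under true values of 0.70/-0.20/0.20) rest on 36 subjects, one observation each and the assumed comparator correlations.

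The defect is that the ordering the SAP names as its goal is never made a prespecified comparison with a measure of uncertainty. It is not a faulty validity gate, because there is none. The correction is worth making because it is cheap and bears on the primary objective.

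**What to change.** In SAP 6.13.1, for PGI-S Shortness of Breath:

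1. Add the expectation that its correlation with Borg exceeds, in absolute value, its correlations with SpO2 and with HR, and exceeds the correlation of Physical Fatigue with Borg.
2. Evaluate these orderings at the times when Borg exists: the pre-ISWT average, ISWT completion, and the change between them. Section 6.13.1 currently names 1 to 5 minutes post-ISWT, when no Borg score is scheduled beyond the one taken within 1 minute of completion.
3. Report each difference between dependent correlations with a 95% CI in Table 14.2.3.2, labelled as descriptive. If visits or periods are pooled, the interval must allow for repeated observations on a subject.
4. State that the ordering, and not the common |r| > 0.30 floor, is the evidence for the stated goal.

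The cost is SAP wording and a few contrasts on data already collected. The drawback is that the expectation becomes harder to support. If the true correlations were 0.60 and 0.35, the interval for their difference would lie above zero in only about 24 to 43% of studies of 36 subjects, for Borg-HR correlations between 0 and 0.5. The report should therefore say in advance that an interval including zero leaves the ordering unresolved and does not refute it.

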6.9 ANALYSIS OF ENDPOINTS

The primary objective is to assess the psychometric properties and performance of the PGI-S items.

The focus of the analyses will be to describe the responsiveness to change of the PGI-S items to the subjects' self-reported symptoms of PAH at the end of the activity and during recovery from the activity. The Sponsor will tabulate the relevant symptom scores and compute change from Baseline (pre-activity) scores for each item. Data may be displayed graphically and will be summarized overall and by cohort and sequence/period (as appropriate).

Additionally, for Cohort A, the sensitivity to a known inhaled treprostinil drug effect will be assessed. Tabulations will be made across sequences/periods for the PGI-S measurements with inhaled treprostinil to PGI-S measurements without inhaled treprostinil. Test-retest assessments for PGI-S measurements will be conducted for Cohort B.

Correlations between the 3 PGI-S questions and with Borg dyspnea scores, oxygen saturation, and HR will be assessed. Data for HR recovery at 1 minute after the ISWT will be examined in an exploratory fashion overall and as related to PGI-S measurements.

The onset and recovery profile for activity-induced symptoms will also be characterized.

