6.12 SUPPORTIVE ANALYSES

6.12.1 *Borg Dyspnea Score*

Summary statistics will be computed to characterize average change and variability overall and by cohort and sequence/period (as appropriate). The pre-ISWT (average of -15 and 0 minutes), post-ISWT at each time point, and pre-post difference for Borg Dyspnea score will be provided. Summary statistics will include the mean, N, standard deviation, median, mode, minimum, maximum, the 25th and 75th percentile values, and 95% confidence intervals for the mean and difference values.

6.12.2 *Pulse Oximetry and Heart Rate*

Summary statistics will be computed to characterize average change and variability overall and by cohort and sequence/period (as appropriate). The pre-ISWT (average of -15 and 0 minutes), post-ISWT at each time point, and pre-post difference for oxygenation and HR will be provided. Summary statistics will include the mean, N, standard deviation, median, mode, minimum, maximum, the 25th and 75th percentile values, and 95% confidence intervals for the mean and difference values.

6.12.3 *ISWT*

Tabulations will be provided by cohort and sequence/period (as appropriate) for the total number of shuttles completed, total distance walked (meters), use of oxygen during ISWT (Yes, No), reason for ISWT ending (Shortness of breath, Physical fatigue, Chest pain, Other), and time since most recent dose of PAH medication (Start time of ISWT - Time of most recent dose of PAH medication).

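### None of the SAP's validity hypotheses separates the Physical Fatigue item from Shortness of Breath, so identical answers to all three PGI-S items could meet all 14

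*SAP*

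**What the plan says.** SAP section 4 names three primary endpoints: the PGI-S items for overall PAH symptoms, shortness of breath and physical fatigue. SAP 6.13.1 states the aim of construct validation as to "demonstrate stronger relationships among measures addressing similar constructs as compared with measures addressing more disparate constructs". The external measures are the Borg score, SpO2 and HR: "Correlations will be computed between PGI-S scores and in Borg Dyspnea scores, oxygen saturation, and HR".

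The level hypotheses are:

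- Overall: "The PGI-S Overall item will be at least moderately correlated", with SpO2 and HR as the comparators.
- Shortness of Breath: "The PGI-S Shortness of Breath item will be at least moderately correlated with the Modified Borg score, oxygen saturation, and HR".
- Physical Fatigue: "The PGI-S Physical Fatigue item will be at least moderately correlated with oxygen saturation and HR".

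The change-score hypotheses use the same comparators with the sign stated, for example "Change in the PGI-S Physical Fatigue item will be at least moderately negatively correlated with change in oxygen saturation".

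Two other places bear on the point. SAP 6.9 says "Correlations between the 3 PGI-S questions and with Borg dyspnea scores, oxygen saturation, and HR will be assessed", with no criterion attached. SAP 6.12.3 tabulates "reason for ISWT ending (Shortness of breath, Physical fatigue, Chest pain, Other". That variable comes from Protocol Appendix 15.2, which has the site record one reason for stopping each walk. The SAP does not link it to the PGI-S.

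**The concern.** SpO2 and HR respond to exertion, and neither measures fatigue. A moderate correlation with them shows that the Fatigue item moves with effort. It does not show that the item captures something other than breathlessness. The aim in 6.13.1 calls for a comparison of correlations, but each hypothesis asks only that one correlation be large enough. The discriminant half of the aim is therefore untested for Fatigue. A report could find every validity hypothesis met and say nothing on whether the Fatigue item adds to the Shortness of Breath item.

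**Working it through.** **1. Count of hypotheses (SAP 6.13.1).**

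| Item | Borg | SpO2 | HR | Level | Change |
|---|---|---|---|---|---|
| Overall | – | yes | yes | 2 | 2 |
| Shortness of Breath | yes | yes | yes | 3 | 3 |
| Physical Fatigue | – | yes | yes | 2 | 2 |
| Total | | | | 7 | 7 |

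Each is a lower bound on |r| (0.30). None compares two items or sets an upper bound.

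**2. Identical answers.** If the three scores are equal for every subject, their correlations with any fourth variable are equal. The Fatigue and Overall lists lie inside the Shortness of Breath list, so all 14 hypotheses hold whenever the five distinct item scores and comparators behind Shortness of Breath's 3 level and 3 change hypotheses all pass. This step needs no assumption about the data.

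**3. The known-groups hypotheses (SAP 6.13.3)** concern WHO class and cohort. They run in the same direction for all items, so they do not separate them either.

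**4. Illustration at N = 36 (all correlations assumed).** Five-category items were simulated. SpO2 and HR were driven by breathlessness only. In the distinct case, latent fatigue correlates 0.5 with breathlessness and Overall is a mix of the two. The entries are the chance that all 7 level hypotheses pass at a single time point.

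| Latent r with Borg, SpO2, HR | Identical items | Distinct fatigue |
|---|---|---|
| 0.7, -0.45, 0.45 | 0.67 | 0.10 |
| 0.8, -0.6, 0.6 | 0.96 | 0.27 |

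With 0.7, -0.2, 0.2, the expected correlations with SpO2 and HR are about 0.19 in size, below 0.30 for all three items, even when answers are identical.

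**5. Would the added analyses fail under identical answers?** Yes. The difference between the Shortness of Breath/Borg and Fatigue/Borg correlations is exactly 0, and so is every subject's Fatigue minus Shortness of Breath score.

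**6. Precision of the stop-reason contrast.** Half-width = t × SD × √(1/n1 + 1/n2), with t(38) = 2.024 and t(34) = 2.032. The documents give no SD for a between-item difference, so 1.0 and 1.3 are assumed. Every walk is taken to end for one of the two reasons.

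| Split | SD 1.0 | SD 1.3 |
|---|---|---|
| 20 / 20 | 2.024 × 1.0 × 0.316 = 0.64 | 0.83 |
| 30 / 10 | 2.024 × 1.0 × 0.365 = 0.74 | 0.96 |
| 31 / 5 | 2.032 × 1.0 × 0.482 = 0.98 | 1.27 |

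**7. Precision of a single correlation.** The 95% limits are tanh(atanh r ± 1.96/√33) at N = 36. For r = 0.5 this gives 0.21 to 0.71, and for r = 0.7 it gives 0.48 to 0.84. The interval for the difference of two dependent correlations also depends on the inter-item correlation, which the documents do not give.

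**The case against.** The strongest reply is that the plan already produces the evidence. SAP 6.9 plans the correlations between the three items. SAP 6.13.1 correlates the PGI-S items with Borg and bases its inferences on the pattern of correlations, not on the bullets alone. Borg is hypothesised only for Shortness of Breath, which hints at a convergent pattern. Identical answers would show up as inter-item correlations of 1 and matching Borg columns. The objective is to characterise the items and formal testing is marked not applicable, so a missing criterion may look like a matter of taste. All of this stands as far as description goes. However, 6.13.1 does set out hypotheses, and none carries the discriminant aim it states.

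The stop reason is also a weak criterion. It is one forced choice, and Appendix 15.2 says the patient can be asked, so it may be the same person's report at nearly the same moment as the rating. The walk leans towards breathlessness: the only patient-reported ending rule is being too breathless, and entry requires a Borg rise of at least 1 point. Some walks will end for chest pain or another reason. The fatigue group may be small. This stands, and it is why the contrast should be supportive only.

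A reader might infer that the trial cannot support three separate questions. The documents do not go that far. The item wording is redacted, SAP 6.11.1 refers to patient interviews, and evidence on content may exist outside these documents. Nor do they show that the inter-item correlations were dropped: 6.9 is current text, and 6.13.1 does not withdraw it.

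**Conclusion.** The point holds in a limited form. SAP 6.13.1 states a discriminant aim, and 0 of its 14 hypotheses test it for the Fatigue item. Identical answers could meet all 14, and would do so whenever Shortness of Breath meets its own. That follows from the lists alone. It would be wrong to say that identical answers must pass: under weak correlations with SpO2 and HR all three items would tend to fail together. The simulated pass rates illustrate one assumed model and are not a property of the plan.

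The stop-reason contrast gives useful precision only if both groups are reasonably large: half-widths of 0.64 to 0.96 with at least 10 in the smaller group, and 0.98 to 1.27 with 5, over assumed SDs of 1.0 to 1.3. The 1-category figure in SAP 6.11.1 is a meaningful change within one item, so it is only a rough yardstick for a between-group contrast of a between-item difference.

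**What to change.** 1. **SAP 6.13.1.** Add the hypothesis that at ISWT completion the Shortness of Breath/Borg correlation exceeds the Fatigue/Borg correlation. Report the difference with a 95% CI for dependent correlations. Name completion as the time point, because the post-walk times now listed are 1 to 5 minutes and Borg is not repeated during recovery. Show the three inter-item correlations at completion in Table 14.2.3.2.
2. **SAP 6.13.3.** Add a supportive known-groups contrast on the Screening walk: the mean Fatigue minus Shortness of Breath score at completion, in subjects who stopped for physical fatigue versus shortness of breath. Give a 95% CI, hypothesise a higher value in the fatigue group, and keep the existing minimum of 5 per group. Screening is the right walk because Day 1 walks are capped at the Screening shuttle count and may end at the cap.
3. **Interpretation.** Describe the Fatigue/SpO2 and Fatigue/HR correlations as association with exertion, not as evidence that the item measures fatigue specifically.

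The cost is SAP wording and a few table rows, with no new data. The downside is that item 2 may be uninformative, or not analysable, if few subjects stop for fatigue.

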6.13.2 Response Frequency Distributions

To examine floor and ceiling effects for each PGI-S item, the percentage of subjects reporting the worst and best possible item scores will be examined in the context of the item-level response frequency distributions. A floor effect occurs if the worst response category (5=Very severe) is the mode of the empirical distribution and at least 2 times the expected percentage of subjects (given a uniform distribution) who select this response category. Similarly, a ceiling effect occurs if the best response category (Not present) is the mode of the empirical distribution and at least 2 times the expected percentage of subjects (given a uniform distribution) who select this response category. In the case of the PGI-S items, which have 5 response categories, the expected percentage of subjects given a uniform distribution is 20%; a floor or ceiling effect would require that more than 40% of the subjects select the worst or best response category, respectively.

PGI-S response frequency distributions will be tabulated and examined at Baseline (pre-ISWT average of -15 minutes and 0 minutes), when symptoms are expected at their minimal level, and post-ISWT (0 minutes), when symptoms are expected at their maximum level. Distributions will be provided for all subjects and visits/periods combined, as well as individually within Cohorts and visits/periods (Screening, Day 1 Period 1, and Day 1 Period 2).

